8.2.6.5. Physical Examination

A physical examination including height and weight will be performed at screening visit by trained medical personnel. Physical examination data will be included in a listing.

8.2.6.6. Suicide Behavior Questionnaire - Revised

The Suicidal Behaviors Questionnaire-Revised (SBQ-R), a brief self-report measure of past suicidal behavior, will be completed by subjects at the Screening visit. SBQ-R data will be included in a listing.

8.2.6.7. Hospital Anxiety and Depression Scale

The Hospital Anxiety and Depression Scale (HADS) measures anxiety and depression in hospital and community settings and has also been validated in the adolescent outpatient population. It is a patient completed questionnaire that establishes the presence and severity of both anxiety (7 questions) and depression (7 questions).

The baseline anxiety total score and depression total score as well as change from baseline at each visit will be summarized by treatment group as described in [Section 8.1.2.1](#). In addition the maximum increase in the anxiety total score and depression total score per subject while on treatment will be summarized by treatment group.

Shift tables for HADs Depression subscore and HADS Anxiety Subscore will be produced by treatment and stratum, as well as overall. The shift will be from baseline to the worst score post-baseline. Both baseline and post-baseline will be categorized to 0-7, 8-10, and 11+. The number and percent of patients who increased to a higher category will be tabulated as well.

If more than one question within a domain (anxiety or depression) is missing, the score will be set to missing. If only one question is missing, the missing response will be imputed with the domain-specific mean based on the remaining questions.

These will be summarized for the following groups:

- Overall study
- 12-16 year old age stratum
- 12-16 year old age stratum, ≤55 kg weight stratum
- 12-16 year old age stratum, >55 kg weight stratum
- 17-19 year old age stratum

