5. STUDY TREATMENTS

5.1. Allocation to Treatment

This is a 52 week, double-blind, parallel group study. Subjects will be randomized to receive 12 weeks of varenicline 1 mg BID, varenicline 0.5 mg BID or placebo in a 1:1:1 ratio using a block randomization within each site. Within each randomized treatment group, subjects who weigh ≤ 55 kg at baseline will receive half the assigned dose strength.

Randomization will be stratified by age group (12-16 vs 17-19). In order to ensure a sufficient number of subjects in the 12-16 year old stratum, the 17-19 year old stratum will be capped at a maximum of 90 subjects.

Investigators will obtain subject identification numbers and study drug assignments utilizing a web-based or telephone call-in drug management system as directed by the sponsor. The web-based or telephone call-in drug management system will provide identification numbers

for the subjects at the screening visit. The web-based or telephone call-in drug management system will also coordinate drug dispensation to subjects at each clinic visit.

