6.2.2. Treatment Phase Clinic Visits (Weeks 1 through 12 and ET₁₂)

Following the Baseline visit, clinic visits will be conducted weekly for 12 weeks. All subjects should have set a target quit date (TQD) to coincide with the Week 1 visit. The Week 1 visit occurs at the end of the first week of the treatment phase. Smoking cessation counseling up to 10 minutes duration will be provided at each clinic visit beginning at Baseline. Whenever possible, counseling should be conducted by the same counselor throughout, so that the relationship builds and brings additional value to the sessions. Every effort should be made to have the subject return on the same day of the week for the clinic visits, thereby keeping visits on time. To accommodate unforeseen circumstances a visit window of ± 3 days can be allowed as long as proper dosing is maintained. If an early termination occurs before the end of Week 12, an early termination visit (ET₁₂) will be conducted. At each of these visits, the following procedures will be conducted:

- Record spontaneously reported adverse events after asking the subjects to respond to a non-leading question such as “How do you feel?”
- Measure and record sitting and orthostatic blood pressure (BP) and sitting, supine and standing pulse rate;
- Have Subject self-administer the HADS ([Appendix 3](#));
- Conduct Neuropsychiatric Adverse Event Interview (NAEI) ([Appendix 4](#)) and record solicited adverse events;
- Complete the Columbia Suicide-Severity Rating Scale (C-SSRS) and record any suicide-related adverse events;
- Record concomitant medications;
- Record any non-drug treatments;
- Review previous week’s Smoking Diary Worksheet with subject and distribute the following week’s; Complete the Nicotine Use Inventory (NUI) based on subject responses ([Appendix 1](#));
- Provide up to 10 minutes of smoking cessation counseling;

- Count and document drug returns;
- Dispense next week's blister pack (except at Week 12 or ET);

The following additional activities will be conducted at Visit Weeks **3, 6, 12**, and early termination:

- Obtain blood samples for safety laboratory tests (week 3, Week 6, and Week 12 or ET);
- Perform urine **pregnancy** test for females (also at **Week 9**);
- Perform urine **drug** test (dipstick at site) (also at **Week 9**);
- Collect blood samples for pharmacokinetic analysis (Week 3, Week 6, and Week 12 or ET);

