7.2.6. Actively Solicited Neuropsychiatric Adverse Events (Appendix 4)

The NAEI will be conducted at every clinic visit from baseline through Week 52. The Neuropsychiatric Adverse Event Interview (NAEI) must be conducted by a qualified mental health professional, who will actively inquire about the following type of adverse events: depression, anxiety, delusions, hallucinations, paranoia, psychosis, mania, panic, agitation, dissociative states, feeling abnormal, hostility, aggression and homicidal ideation. If a subject has a positive response to any item on the NAEI, a determination will be made by the investigator as to whether this meets criteria for an adverse event. If it does meet criteria as an adverse event it will be recorded on the adverse event pages of the Case Report Form. Dosing must be stopped if an adverse event moderate or severe in nature is elicited through this interview.

Hospital Anxiety and Depression Scale (HADS) (Appendix 3).

The Hospital Anxiety and Depression Scale (HADS) measures anxiety and depression in hospital and community settings and has also been validated in the adolescent outpatient population.¹⁷ It is a patient completed questionnaire that establishes the presence and severity of both anxiety (7 questions) and depression (7 questions) (Appendix 3).

The HADS is a self-report scale and contains 14 items rated on 4-point Likert-type scales. Two subscales assess depression and anxiety. The HADS will be completed by the subject at every clinic visit through Week 52. Dosing must be stopped if the HADS score for either depression or anxiety is ≥ 15 .

Subjects' self-report via the HADS is aimed to more fully characterize potential depression and anxiety related events. These additional measurements will be collected and evaluated in a different manner than the observed or volunteered adverse events. No attempt will be made to resolve any apparent discrepancies between observed or volunteered adverse events and the additional data collected from subjects using the HADS self-report. These additional data will be presented in separate tables, separate figures, and separate data listings, and will be reviewed in the final study report.

Adverse event incidence rates will not be calculated from the self-reported HADS data but rather from the spontaneously reported information, the NAEI and the CSSRS data described above, recorded on the adverse event pages from the Case Report Form (CRF).

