8.2.6.8. Columbia Suicide Severity Rating Scale (C-SSRS)

The Columbia Suicide Severity Rating Scale (CSSR-S) is a set of suggested questions designed to elicit information about passive or active suicidal ideation, active suicidal intent, and self-injurious behavior.

Frequency counts and percents for the C-CASA categories will be displayed in figures as well as tables for screening (Lifetime), baseline, treatment emergent, and follow up findings by treatment group. Treatment emergent responses are those between the date of first dose of study medication and the date of last dose plus 30 days. If last dose plus 30 days falls within the look back period for the ‘since the last visit’ administration of the C-SSRS, the responses are considered treatment emergent. Follow Up is all responses more than 30 days after the date of last dose. Listings will include both C-SSRS observed data as well as C-CASA categories.

These will be summarized for the following groups:

- Overall study
- 12-16 year old age stratum
- 12-16 year old age stratum, ≤ 55 kg weight stratum
- 12-16 year old age stratum, > 55 kg weight stratum
- 17-19 year old age stratum

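### The HADS shift table has no time window, so on-treatment and follow-up scores are pooled in the only categorical HADS summary

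*SAP*

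**What the plan says.** SAP 8.2.6.7 plans four HADS outputs by treatment group:

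- Baseline scores and by-visit change: "change from baseline at each visit will be summarized by treatment group".
- A per-subject maximum, limited to the treatment period: "maximum increase in the anxiety total score and depression total score per subject while on treatment".
- Shift tables for each subscale, under the rule "The shift will be from baseline to the worst score post-baseline". The bands are given as "Both baseline and post-baseline will be categorized to 0-7, 8-10, and 11" and above, so the top band is open-ended.
- The number and percent of subjects who move to a worse band.

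The last two carry no time limit. On collection, Protocol 7.2.6 says "The HADS will be completed by the subject at every clinic visit through Week 52". On treatment length, Protocol 5.1 says "Subjects will be randomized to receive 12 weeks of varenicline".

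The next section, SAP 8.2.6.8, does split the C-SSRS by period. Responses from first dose to last dose plus 30 days are treatment emergent, and the remainder is separate: "Follow Up is all responses more than 30 days after the date of last dose". SAP 8.2.6.1 sets the same 30-day lag for adverse events.

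**The concern.** Safety and tolerability are part of the primary objective, and neuropsychiatric symptoms are the main post-marketing concern that the protocol describes. Exclusion criterion 8 removes subjects scoring 8 or more on either HADS subscale, so nearly all subjects should start in the lowest band. In practice the shift table therefore answers one question: what share of each arm reached 8-10, or 11 and above?

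With no window, that share mixes two periods. A subject whose score first rises at Week 44, 32 weeks after the Week 12 visit, counts the same as one whose score rises at Week 4 on drug. A subject who rises to 8-10 on drug and to 11 or more in follow-up appears only in the top band. The reader cannot separate these cases, and no other planned output counts subjects crossing a HADS band on treatment. Two programmers could also read the rule differently and produce different tables.

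**Working it through.** The documents state no figure for this table, so there is none to reproduce. The check counts visits and then works through an illustration.

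**Visits at which HADS is scheduled**

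- Treatment: "Following the Baseline visit, clinic visits will be conducted weekly for 12 weeks" (Protocol 6.2.2), which gives 12 visits.
- Follow-up clinic visits (Protocol Sections 3 and 6.3.1): Weeks 13, 14, 15, 16, 20, 28, 36, 44 and 52, which gives 9. The schedule of activities has no HADS at the telephone contacts.
- Total: 12 + 9 = 21. The share after Week 12 is 9/21 = 43%.
- Visits inside the 30-day lag for a subject who completes treatment: Week 16 is nominally (16 − 12) × 7 = 28 days after Week 12 and Week 20 is 56 days after. Weeks 13-16 (4 visits) therefore fall inside, and 9 − 4 = 5 fall outside. 5/21 = 24%.

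Subjects may stop drug early and remain in the study (Protocol 6.4). They would have more off-drug visits than this.

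**Effect on the table**

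Let p be the probability of moving up a band on treatment and q the probability of doing so in the added follow-up visits. Take q as equal in both arms and independent of on-treatment status. Then:

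- P(shift in the table) = 1 − (1 − p)(1 − q)
- Risk difference in the table = (p_varenicline − p_placebo) × (1 − q)

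The documents give no HADS shift rates. **Assumed:** p = 10% on placebo and 20% on varenicline, with the placebo per-visit rate continuing unchanged after Week 12 in both arms. The per-visit probability of no shift is 0.90^(1/12), so q = 1 − 0.90^(k/12) for k added visits:

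- k = 9: q = 1 − 0.90^0.75 = 7.6%
- k = 4 (lag window): q = 1 − 0.90^(1/3) = 3.5%

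| Window | Placebo | Varenicline | Risk difference (points) | Relative risk |
|---|---|---|---|---|
| Weeks 1-12 only | 10.0% | 20.0% | 10.0 | 2.00 |
| To last dose + 30 days (16 visits) | 13.1% | 22.8% | 9.7 | 1.74 |
| All visits to Week 52 (21 visits) | 16.8% | 26.1% | 9.2 | 1.55 |

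For the last row: 1 − 0.90 × 0.924 = 16.8% and 1 − 0.80 × 0.924 = 26.1%.

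**Range over the assumptions**

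- 10% against 20%, with q set directly: q = 5% gives a relative risk of 1.66 and a difference of 9.5 points; q = 15% gives 1.36 and 8.5; q = 30% gives 1.19 and 7.0.
- 5% against 15%, constant per-visit rate, all visits: relative risk from 3.00 to 2.12, difference from 10.0 to 9.6 points.
- 10% against 25%, same rule: relative risk from 2.50 to 1.82, difference from 15.0 to 13.9 points.

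The relative risk falls noticeably in every case. The risk difference falls only by the factor 1 − q.

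**The case against.** The strongest reply is that the treatment period is already visible. The same SAP section gives change from baseline at each visit and the maximum increase on treatment. Treatment-emergent adverse events and the C-SSRS have their own windows. A worst-score rule cannot drop an on-treatment shift; it can only add later ones. Protocol Section 3 names neuropsychiatric monitoring as a purpose of follow-up, so a whole-study table is legitimate. Safety analyses are descriptive, so no test loses power.

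Most of this stands, and it limits the size of the point. It does not remove it. The two other HADS outputs summarise scores and do not count subjects crossing a band. Protocol 7.2.6 also rules out deriving adverse event rates from HADS, so the adverse event tables do not fill the gap.

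Some stronger readings are tempting but unsupported:

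- *That 40 of 52 weeks in the table (77%) are off drug.* HADS asks about the past week only, so most follow-up weeks are never sampled. The relevant figures are 9 of 21 visits, or 5 of 21 beyond the lag.
- *That the SAP specifies scores to Week 52.* It does not. That is the literal consequence of an absent limit.
- *That unequal retention biases the table in a known direction.* Any worst-score table depends on the number of assessments, including one limited to treatment, and the documents show no direction.
- *That the top band should be split at 15, the region where dosing stops.* Protocol 6.4 stops dosing at 15 or more for anxiety but above 15 for depression, while Protocol 7.2.6 says 15 or more for either. These passages contradict each other and must be reconciled. A 15-and-above band is not part of this point.

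**Conclusion.** The point holds as a missing window with a modest effect. Read literally, the rule pools treatment and follow-up in the only categorical HADS output, against the SAP's own practice for the C-SSRS and for the maximum HADS increase. What is lost is the ability to say when a shift happened and, for some subjects, how severe it was on treatment.

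In the main illustration, moving from all visits to the lag window changes the relative risk from 1.55 to 1.74 and the risk difference by about half a point. A reader might infer that an on-treatment mood signal would be hidden. The documents do not support that, because on-treatment shifts stay in the count and other outputs show the treatment period.

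The numbers rest on assumed shift rates, equal follow-up rates in the arms and independence between periods. If the same subjects shift in both periods, the attenuation is smaller. If stopping the drug itself affects mood, the pooled table could move the other way. Either possibility is a reason to show the periods separately.

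**What to change.** In SAP 8.2.6.7, produce the shift table and the category-increase count for each subscale in two periods:

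1. From first dose to last dose plus 30 days, the window the SAP already uses for the C-SSRS.
2. After last dose plus 30 days.

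Base the window on each subject's actual last dose, so that those who stop drug early are placed correctly. Use as denominator the number of subjects with at least one HADS assessment in the period, and print it. Keep the all-visit table as supportive and label its window.

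The data are already collected. The cost is a change of SAP wording and a few extra descriptive tables for two subscales across five reporting groups, some of which will be small.

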8.2.6.8. Columbia Suicide Severity Rating Scale (C-SSRS)

The Columbia Suicide Severity Rating Scale (CSSR-S) is a set of suggested questions designed to elicit information about passive or active suicidal ideation, active suicidal intent, and self-injurious behavior.

Frequency counts and percents for the C-CASA categories will be displayed in figures as well as tables for screening (Lifetime), baseline, treatment emergent, and follow up findings by treatment group. Treatment emergent responses are those between the date of first dose of study medication and the date of last dose plus 30 days. If last dose plus 30 days falls within the look back period for the ‘since the last visit’ administration of the C-SSRS, the responses are considered treatment emergent. Follow Up is all responses more than 30 days after the date of last dose. Listings will include both C-SSRS observed data as well as C-CASA categories.

These will be summarized for the following groups:

- Overall study
- 12-16 year old age stratum
- 12-16 year old age stratum, ≤ 55 kg weight stratum
- 12-16 year old age stratum, > 55 kg weight stratum
- 17-19 year old age stratum

Appendix 1. Neuropsychiatric Adverse Events

Neuropsychiatric adverse events will be the MedDRA preferred terms included below.

Anxiety:

HLT Name	PT Name
Adjustment disorders	Adjustment disorder with anxiety
Anxiety disorders NEC	Anxiety disorder Anxiety disorder due to a general medical condition Generalised anxiety disorder Neurosis
Anxiety symptoms	Activation syndrome Anticipatory anxiety Anxiety Nervousness Stress Tension
Fear symptoms and phobic disorders (incl social phobia)	Autophobia
Impulse control disorders	Impulse-control disorder Impulsive behaviour Pyromania Trichotillomania
Obsessive-compulsive disorders and symptoms	Compulsions Obsessive thoughts Obsessive-compulsive disorder
Panic attacks and disorders	Limited symptom panic attack
Stress disorders	Acute stress disorder Burnout syndrome Post-traumatic stress disorder
Behaviour and socialisation disturbances	Impatience
Anxiety symptoms	Somatoform disorder cardiovascular

<continued next page>

Anxiety:

HLT Name	PT Name
Fear symptoms and phobic disorders (incl social phobia)	Acrophobia Agoraphobia Animal phobia Arachnophobia Claustrophobia Dysmorphophobia Fear Fear of animals Fear of closed spaces Fear of crowded places Fear of death Fear of disease Fear of eating Fear of falling Fear of injection Fear of open spaces Fear of pregnancy Fear of weight gain Haphephobia Hydrophobia Noctiphobia Nocturnal fear Nosophobia Ochlophobia Osmophobia Paruresis Performance fear Phagophobia Phobia Phobia of driving Phobia of exams Phobia of flying Phobic avoidance Phonophobia Photaugiaphobia Social fear Social phobia Thanatophobia

Depression:

HLT Name	PT Name
Adjustment disorders	Adjustment disorder with depressed mood Adjustment disorder with mixed anxiety and depressed mood
Behaviour and socialisation disturbances	Asocial behaviour Social avoidant behaviour
Depressive disorders	Agitated depression Depression Dysthymic disorder Major depression Menopausal depression Postpartum depression
Mood alterations with depressive symptoms	Anhedonia Decreased interest Depressed mood Depressive symptom Feeling guilty Feeling of despair Feelings of worthlessness Morose Negative thoughts Psychomotor retardation Tearfulness
Mood disorders NEC	Apathy Boredom Laziness Mood disorder due to a general medical condition Seasonal affective disorder
Personality disorders NEC	Self esteem decreased
Abnormal behaviour NEC	Regressive behaviour
General signs and symptoms NEC	Crying

Feeling Abnormal:

HLT Name	PT Name
Abnormal behaviour NEC	Abnormal behavior
Mental disorders NEC	Mental disorder Mental status changes Dyslogia
Confusion and disorientation	Confusional state Disorientation
Emotional and mood disturbances NEC	Emotional disorder Emotional distress
Behaviour and socialisation disturbances	Personality change
Mental impairment (excl dementia and memory loss)	Mental impairment
Psychiatric symptoms NEC	Psychiatric symptom Trance
Nervous system disorders NEC	Nervous system disorder
Feelings and sensations NEC	Feeling drunk Feeling abnormal
Disability issues	Activities of daily living impaired Impaired driving ability Impaired work ability Bedridden Disability
General signs and symptoms NEC	Performance status decreased Impaired self-care
Decreased physical activity levels	Catatonia
Dementia NEC	Pseudodementia
Dissociative states	Depersonalisation Dissociation Dissociative amnesia Dissociative disorder Dissociative fugue Dissociative identity disorder
Perception disturbances	Derealisation
Parasomnias	Confusional arousal
Disturbances in consciousness NEC	Altered state of consciousness Consciousness fluctuating
Emotional and mood disturbances NEC	Mood altered

<continued next page>

Feeling Abnormal:

HLT Name	PT Name
Partial complex seizures	Dreamy state
Thinking disturbances	Bradyphrenia Circumstantiality Confabulation Derailment Ideas of reference Illogical thinking Impaired reasoning Loose associations Magical thinking Morbid thoughts Obsessive rumination Perseveration Poverty of thought content Tachyphrenia Tangentiality Thinking abnormal Thought blocking

Hostility:

HLT Name	PT Name
Behaviour and socialisation disturbances	Antisocial behaviour Belligerence Hostility
Impulse control disorders	Intermittent explosive disorder
Personality disorders with dramatic behaviour (Cluster B)	Psychopathic personality

Agitation:

HLT Name	PT Name
Anxiety symptoms	Agitation
Increased physical activity levels	Restlessness
Mental impairment (excl dementia and memory loss)	Disturbance in attention
Dyskinesias and movement disorders NEC	Hyperkinesia

Aggression:

HLT Name	PT Name
Criminal activity	Homicide Incest Physical abuse Physical assault Sexual abuse Spousal abuse Verbal abuse
Behaviour and socialisation disturbances	Aggression Violence-related symptom
Personality disorders with dramatic behaviour (Cluster B)	Antisocial personality disorder
Emotional and mood disturbances NEC	Anger Dysphoria

Delusions:

HLT Name	PT Name
Delusional symptoms	Cotard's syndrome Delusion Delusion of grandeur Delusion of reference Delusion of replacement Delusions, mixed Depressive delusion Erotomantic delusion Jealous delusion Persecutory delusion Somatic delusion Thought broadcasting Thought insertion Thought withdrawal
Delusional disorders	Alice in wonderland syndrome Delusional disorder, erotomantic type Delusional disorder, grandiose type Delusional disorder, jealous type Delusional disorder, mixed type Delusional disorder, persecutory type Delusional disorder, somatic type Delusional disorder, unspecified type
Perception disturbances	Deja vu Delusional perception Jamais vu
Behaviour and socialisation disturbances	Grandiosity

Hallucination:

HLT Name	PT Name
Perception disturbances	Hallucination Hallucination, auditory Hallucination, gustatory Hallucination, olfactory Hallucination, synaesthetic Hallucination, tactile Hallucination, visual Hallucinations, mixed Illusion Somatic hallucination
Narcolepsy and associated conditions	Hypnagogic hallucination Hypnopompic hallucination

Mania:

HLT Name	PT Name
Thinking disturbances	Flight of ideas
Mood alterations with manic symptoms	Hypomania Mania
Emotional and mood disturbances NEC	Elevated mood Euphoric mood
Personality disorders NEC	Self esteem inflated
Bipolar disorders	Bipolar disorder Bipolar I disorder Bipolar II disorder Cyclothymic disorder
Affect alterations NEC	Affect lability
Behaviour and socialisation disturbances	Disinhibition
Fluctuating mood symptoms	Mood swings

Panic:

HLT Name	PT Name
Panic attacks and disorders	Panic attack Panic disorder Panic disorder with agoraphobia Panic disorder without agoraphobia Panic reaction
Abnormal behaviour NEC	Breath holding

Paranoia:

HLT Name	PT Name
Behaviour and socialisation disturbances	Paranoia
	Suspiciousness
Personality disorders with eccentric behaviour (Cluster A)	Paranoid personality disorder
Psychiatric symptoms NEC	Hypervigilance

Psychosis:

HLT Name	PT Name
Affect alterations NEC	Flat affect Inappropriate affect
Brief psychotic disorder	Brief psychotic disorder with marked stressors Brief psychotic disorder without marked stressors Transient psychosis
Psychotic disorder NEC	Acute psychosis Hysterical psychosis Psychotic behaviour Psychotic disorder Psychotic disorder due to a general medical condition Reactive psychosis Shared psychotic disorder
Schizoaffective and schizophreniform disorders	Schizoaffective disorder Schizoaffective disorder bipolar type Schizoaffective disorder depressive type Schizophreniform disorder
Schizophrenia NEC	Schizophrenia Schizophrenia simple Schizophrenia, catatonic type Schizophrenia, disorganised type Schizophrenia, paranoid type Schizophrenia, residual type Schizophrenia, undifferentiated type
Personality disorders with eccentric behaviour (Cluster A)	Schizotypal personality disorder
Behaviour and socialisation disturbances	Negativism

Homicidal Ideation:

HLT Name	PT Name
Behaviour and socialisation disturbances	Homicidal ideation

Suicidal Behavior:

HLT Name	PT Name
Suicidal and self-injurious behaviour	Intentional self-injury Self injurious behaviour Suicidal behaviour Suicide attempt

Suicidal Ideation:

HLT Name	PT Name
Suicidal and self-injurious behaviour	Self-injurious ideation Suicidal ideation

Suicide:

HLT Name	PT Name
Suicidal and self-injurious behaviour	Completed suicide
Depressive disorders	Depression suicidal

